 LR : low risk
 SA : spontaneous abortion

Table 2 : THE RELATIONSHIP BETWEEN ANTENATAL INTERVENTIONS AND OUTCOMES (b)

INTERVENTION	IMPACT			INDICATOR	
	IMMEDIATE	INTERMEDIATE	DELAYED	PROCESS	IMPACT
Classification of risk level, 1st visit (including clinical history)	Classification of women to receive care at clinic (new programme) or other level	Provide care according to health needs	Reduce perinatal/ maternal mortality	% false positive and false negatives of the screening method	Reduction in risk specific perinatal mortality
Continuous risk assessment (development of symptoms signs)	Identification of women with need for special care	Refer to adequate level of care	Reduce negative pregnancy outcomes related to these conditions	% women referred for the clinic; % women admitted in emergency services	Reduction of perinatal mortality related to these conditions
Maternal weight (follow-up visits)	Detection abnormal weight gain patterns; referral to nutrition clinics of low weight gain/underweight women	Improve maternal nutritional status; reduce IUGR	Reduce maternal depletion syndrome; maternal overweight	% women with abnormal weight gain patterns detected	Rate of reduction in IUGR; rate of reduction of women with very low weight post partum
Measure hemoglobin to all women at 30th week of pregnancy	Detection women in need of higher Fe doses; detection women with hemoconcentration	Improve maternal nutrition/ health status; increase placental circulation and reduce fetal growth retardation	Improve maternal nutritional status; reduce LBW/IUGR; reduce risk of maternal death related to hemorrhage	% high risk women detected with very low hemoglobin levels; % women with higher Fe doses	Rate of postpartum hemorrhage; rate of women needing blood transfusion; maternal mortality intrapartum/ postpartum
Antibody titration to mother of Rh(-); newborn hemolytic diseases (1st visit)	Refer to hospital	Treatment of Rh(-) fetal anemia	Reduce fetal death	% of referred women	Reduction fetal/neonatal mortality
Prophylaxis for Rhesus (30 weeks)	Post partum prevention	—	Reduce Rh(-) disease	% Rh(-) mother with γ globulin postpartum	

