Only one routine vaginal examination during pregnancy is recommended, including taking a sample for Pap smear if this is routinely performed in the clinics and screening for symptomatic STDs (Wangford & Smaill, 1989). It could be postponed until the second visit if the doctor or midwife feels that the women or her companion would not accept this. In women with (a history of) bleeding in the present pregnancy, vaginal examination should not be performed at the clinic after the first trimester, and the patient should be referred for ultrasonography examination, if available at the hospital, to exclude placenta previa (Chamberlain, 1992).

As routine iron supplementation will be given to all women, hemoglobin would be determined only at 32 weeks (the third visit) unless there are clinical signs of anemia.

Easy access to care in case of need is essential in the new package. This must be guaranteed through written information about which place and which person to contact, with telephone numbers if available, on a 24-hour basis.

Individual instruction is an essential element of antenatal care. Sufficient time must be set aside for communication and planning, especially at the first visit. We anticipate more available time for each individual visit as a result of the lower number of visits for low risk (the majority of) women, in addition to shorter waiting times and immediate medical availability for unscheduled visits. It will include general information about pregnancy and delivery and individual counselling if demanded or deemed necessary. Otherwise, patients can

go home sooner. The individual counselling will be specific to each woman's condition and emphasis will be on listening to her problems. It should include simple written instructions in the local language, even to illiterate mothers (often family members or neighbors can read). This activity will be focused on instruction for actions to be taken in case of pregnancy-related emergencies. Less emphasis will be placed on formal social support or general health education, as several randomized controlled trials have failed to demonstrate major benefits (Oakley, 1990; Villar et al., 1992).

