- third stage excessive bleeding
- puerperal sepsis
- gestational diabetes

III.C. Special perinatal (fetal, newborn) complications and events in previous pregnancies (specify and validate as for III.B.):

- twins, higher order multiples
- low birth weight (LBW): < 2500 g, or to be defined
- intrauterine growth retardation (if feasible)
- rhesus-antibody affection (erythroblastosis, hydrops)
- malformed, chromosomally abnormal child
- macrosomia (> 4500 g) newborn
- resuscitation, other treatment of newborn
- perinatal, neonatal, infant death (also: later death).

IV. History of present pregnancy

- IV.A. Date of last menstrual period (LMP). Certainty of dates (by regularity and accuracy of recall, other relevant information).
- IV.B. Habits: smoking/chewing tobacco, alcohol, drugs (frequency, quantity).
- IV.C. Any untoward events (pain, vaginal bleeding of threatened miscarriage, hemorrhage).
- IV.D. History of malaria attacks.

V. Physical examination

- V.A. Weight and height; blood pressure (BP). Chest, heart auscultation, Symphysis to fundus distance (in centimeters). All women.
- V.B. Signs of severe anemia: complexion, fingernails, conjunctiva, oral mucosa, tip of tongue. Shortness of breath. All women.
- V.C. Consider vaginal examination, especially if untoward events are positive (IV.C)

VI. Special tests

- VI.A. Urine: protein, multiple dipstick for bacteriuria.
- VI.B. Blood: syphilis (rapid test) result while waiting in the clinic. If positive: treat.
Hb: only if signs of severe anemia.
Blood type and rhesus.

VII. Assessment and referral

- VII.A. Determine the expected date of delivery based on LMP and all other relevant information. Use 280-day rule (LMP + 280 days). Observe: same women will refer to the date of the first missed period when asked about LMP, which may lead to miscalculation of term by four weeks.
- VII.B. Risk assessment (advice: see IX): Women are classified as eligible for the basic components of the new antenatal package or in need of special care and to be followed at the clinic or hospital (Classifying form, Appendix I).

For the following conditions, if diagnosed, is recommended:

- diabetes: refer, must have continued higher level care
- heart disease: refer
- renal disease: refer
- epilepsy: advice on continued medication
- drug abuse: special care
- signs of severe anaemia and Hb < 70 g/dl: higher iron dose, or refer if shortness of breath
- HIV positive: counsel on risk to offspring; refer

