- risk of genetic disease, and possibility of further checks: refer
- primigravida: hospital delivery
- previous stillbirth: refer
- previous growth-retarded fetus (validated IUGR): refer to higher level of care
- hospital admission for eclampsia/pre-eclampsia: refer
- previous cesarean section: stress hospital delivery
- high blood pressure (> 140/90 mmn Hg) refer for evaluation
- Body Mass Index (BMI) (Weight in Kg/height (m)²) (refer for nutritional evaluation if BMI < 18.5 or > 32.3 kg/m²).

Please note that the BMI cut off point < 18.5 is based on calculations of chronic energy deficiency in adults (James et al., 1988) that require validation against maternal and infant outcomes. This value unfortunately requires also local adaptation; for example the mean BMI in a sample of Guatemalan women (N = 12,786) was 22.5 + 3.14 kg/m² (Flegal K et al., 1993). It is possible that if a local weight for height reference chart is available it can be incorporated in the clinical procedures, as it has been shown that the use of body mass index does not represent an advantage over no power-type indexes (weight/height) (Flegal et al., 1993). If this is not the case, pre-pregnancy maternal weight (using local cut-off points) is recommended for evaluation of the nutritional status during the first antenatal visit.

- evidence of pre-eclampsia: refer to higher level of care, or hospitalize.
- suspicion of fetal growth retardation (symphysis-to-fundus distance too low): arrange extra visit at week 29.
- mother does not feel fetal movement: use hand-held doppler for detection of fetal heart sound. If negative, refer to hospital.

VIII. Intervention

- VIII.A. Iron: continue, all. If Hb (see VII.A.) < 70 g/l: higher dose, or if with symptoms, refer.
- VIII.B. If bacteriuria at first visit was treated and test still (+), refer.
- VIII.C. If bleeding, refer.

IX. Advice, questions & answers, and appointment

- IX.A. Repeat all advice given at first visit (A-E).
- IX.B. Questions & answers: time for free communication.
- IX.C. Advice on where and whom to call in case of emergency, as at first visit.
- IX.D. Appointment: third visit: at (close to) 32 weeks.

X. Record keeping

- X.A. Office record.
- X.B. Home based record.

The Third Visit

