V.F. Other alarming signs of disease: shortness of breath; cough, etc.

V.G. If bleeding or spotting; refer.

V.H. Breast examination.

VI. Special test

VI.A. Urine: protein for nulliparous or high risk multiparous.

VI.B. Blood: Hb, all.

VII. Assessment and referral

VII.A Reassess risk based on evidence since second visit and observations at present visit:

- untoward symptoms: referral as required
- evidence of preeclampsia; refer to special unit in the clinic, or hospitalize
- suspicion of fetal growth retardation: (symphysis-to-fundus distance too short): refer and arrange for delivery
- suspicion of twins: refer for confirmation, arrange delivery
- urine test positive for protein: refer
- if Hb continuously < 70 g/l: refer and arrange for delivery
- if Hb > 130 g/l: new appointment at 36 weeks, to check fetal growth, blood pressure and proteinuria.

VIII. Intervention

VIII.A. Iron: continue, all. If Hb on first test < 70 g/l, refer.

VIII.B. If bleeding, refer.

VIII.C. Tetanus toxoid, second injection.

IX. Advice, questions & answers, and appointment

IX.A. Repeat advice given at first and second visits.

IX.B. Advice on measures, action in case of (threatened) labour.

IX.C. Questions & answers: time for free communication.

IX.D. Reconfirm written information on where and whom to call in case of emergency or any other need.

IX.E. Recommendations on lactation, contraception and the importance of the postpartum visit.

IX.F. Appointment: fourth visit: at (or close to) 38 weeks.

X. Record keeping

- X.A. Office record.
- X.B. Home based record.

The Fourth Visit

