16. Any previous surgery on reproductive tract? (Myomectomy, removal of septum, cone biopsy, classical CS, cervical cerclage)	
1 = No 2 = Yes	
17. Iso-immunization Rh(-) in current or in previous pregnancy	
1 = No 2 = Yes	

ANTENATAL CARE	
18. First day of the last normal menstrual period	day month year 
19. Date of first antenatal visit	day month year 
20. Visits to antenatal care or hospital outpatient clinics	Gestational age
a) 1st visit	Completed weeks 
b) 2nd visit	
c) 3rd visit	
d) 4th visit	
e) 5th visit	
21. Total number of visits:	
a) to the original antenatal care clinic	
b) to any other antenatal clinic	
c) to a hospital high risk clinic	

163

Subject number

Grid for subject number

22. Tetanus immunization

- 1 = No
2 = Incomplete (1 dose)
3 = Yes (complete 2 doses)
4 = Previously immunized (1 dose)

23. a) Iron supplementation

- 1 = No 2 = Yes
3 = Contraindicated

b) If Yes, gestational age when supplementation started Weeks

24. a) Referred to higher level of antenatal care

- 1 = No 2 = Yes

If No, go to Q 26

1st 2nd

b) If Yes, gestational age at referral

Grid for gestational age at referral

25. Principal reason for referral

- 1 = No 2 = Yes

- a) Pregnancy induced hypertension
b) Pre-eclampsia
c) Severe anaemia (< 70 g/l)
d) Chronic hypertension
e) Uterine height low for gestational age
f) Malpresentation or breech
g) Multiple gestation
h) Pyelonephritis or urinary infection
i) Vaginal bleeding
j) Diabetes mellitus
k) Cardiac disease
l) Chronic respiratory conditions
m) Renal disease
n) Pelvic mass
o) Isoimmunization Rh(-)
p) Other

Grid for principal reason for referral (1st and 2nd)

26. After referral, the mother

- 1 = Continued care at higher level of antenatal care
2 = Was referred back to the original antenatal care clinic (or level)
3 = Was scheduled for hospital admission (complete Form 2 - AHA)

Grid for referral outcome (1st and 2nd)

27. Any hospital admission during the antenatal period

- 1 = No 2 = Yes

MATERNAL EVENTS DURING PREGNANCY

28. Hypertensive disorders of pregnancy

- 1 = No 2 = Yes

- a) Only hypertension, no treatment
b) Only hypertension with treatment or referral
c) Pre-eclampsia (hypertension and proteinuria)

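### The haemoglobin limit for a higher iron dose is printed in g/dl at the first visit and in g/l at the second, a tenfold conflict that is probably a unit slip and should be reconciled

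*Protocol*

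**What the plan says.** In Protocol section 4.4.2, content of the first visit, item VII.B lists conditions and the recommended response. The anaemia line reads "signs of severe anaemia and Hb < 70 g/dl: higher iron dose, or refer if shortness of breath". Item VI.B of the same visit restricts the test: "Hb: only if signs of severe anemia".

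The next list of visit content ends by booking the third visit, so it belongs to the second. Its iron line reads "VIII.A. Iron: continue, all. If Hb (see VII.A.) < 70 g/l: higher dose, or if with symptoms, refer".

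At the third visit the iron line is "VIII.A. Iron: continue, all. If Hb on first test < 70 g/l, refer", and item VII.A of that visit also uses 70 g/l, again for referral. In Appendix I the Summary form lists "c) Severe anaemia (< 70 g/l") as a reason for referral (Q25) and as a condition at admission in labour (Q35). Its haemoglobin fields (Q31 and Q39) are in g/l.

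On timing, Table 2(b) in section 4.4.1 has "Measure hemoglobin to all women at 30th week of pregnancy", while the text on the first visit in section 4.4.2 says "hemoglobin would be determined only at 32 weeks (the third visit) unless there are clinical signs of anemia".

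**The concern.** The line sits inside the randomised intervention and decides whether a woman receives more iron or is referred. The two visits attach the same pair of actions to limits that differ only in the unit, and the units differ by a factor of ten. A limit that every tested woman meets does no work. Table 2(c) says the first-visit test is meant to pick out candidates for more iron and to corroborate the clinical impression. With the printed limit it can do neither.

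What is at stake is the accuracy of a treatment rule in a package designed to be run largely by staff below physician level from a simple set of rules. The share of women on a high iron dose is also one of the process indicators in Table 2(c), so the rule bears on how the intervention is described.

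**Working it through.** No power, alpha or event calculation is involved. The check is a unit conversion and a comparison of the lines.

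**Inputs, all from the protocol**

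- First visit, VII.B: limit 70 g/dl, combined with signs of severe anaemia; action is a higher dose or referral.
- First visit, VI.B: test done only when signs of severe anaemia are present.
- Second visit, VIII.A: limit 70 g/l; action is a higher dose or referral.
- Third visit, VII.A and VIII.A: limit 70 g/l; action is referral.
- Summary form Q25c and Q35c: 70 g/l as a reporting category.
- Third visit: haemoglobin above 130 g/l is treated as high.

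**Step 1, convert.** 1 g/dl = 10 g/l, so 70 g/dl = 70 × 10 = 700 g/l.

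**Step 2, compare.** 700 / 70 = 10. Against the protocol's own mark for a high value, 700 / 130 = 5.4. No plausible result reaches the printed first-visit limit.

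**Step 3, trace the first-visit rule.** The action requires clinical signs and a result below the limit. The test is done only when signs are present. If every result lies below 700 g/l, the second condition is always true and the rule reduces to clinical signs alone.

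**Step 4, one worked case.** Take a woman with signs and a haemoglobin of 90 g/l. At the first visit 90 < 700, so the printed condition is met. Under the second-visit line 90 > 70, so it is not.

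**Step 5, where the conflict lies.** Only the first- and second-visit lines set a limit for the higher dose. The third-visit lines use 70 g/l for referral and the form uses it for classification. They show that g/l is the unit used elsewhere, but they are not further versions of the dose rule.

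**Step 6, timing.** Week 30 in Table 2(b) against week 32 in the visit schedule is a nominal difference of 32 − 30 = 2 weeks.

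**The case against.** The strongest reply is that this is a self-evident typing error. The other haemoglobin limits and the form fields are in g/l, and a limit of 700 g/l is so far out of range that staff could hardly use it. Providers work from the Manual of Clinical Activities, which is not in the document, and the clinic checklist in Appendix I carries no g/dl figure. The rule also requires clinical signs, so even a literal reading reaches few women. All of this stands, and it limits the weight of the point. It does not make the printed line correct.

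The text available here also runs from the first-visit assessment list straight into second-visit content. A first-visit intervention item on iron may exist that cannot be seen. That absence is not held against the plan, but it means the complete first-visit rule cannot be confirmed.

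Three stronger readings are tempting, and the protocol does not support them:

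- **Women were over-treated, or clinics applied the rule unevenly.** No passage reports how any clinic applied the line.
- **The size can be read from the Khon Kaen results.** In Table 25, 296 of 6,354 women (4.7%) had a lowest haemoglobin below 90 g/l, and one might set this against 100% of tested women meeting the printed limit. The first figure covers all women in both arms, at any time in pregnancy. The second covers only women tested at the first visit because of signs. The denominators do not match.
- **The primary maternal index is distorted.** Severe postpartum anaemia was 6.3% and the index 8.3%, a ratio of 6.3 / 8.3 = 0.76. That is at most the share of index cases with this component. It does not measure what the first-visit rule affects, and routine iron goes to all women anyway.

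The absence of a separate higher-dose step at the third visit could also be called a contradiction. Referral there is a clinical design choice and can be squared with the test's purpose.

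**Conclusion.** The point holds in a limited form. The first-visit and second-visit lines give limits for the same action that differ exactly tenfold, and the first-visit line cannot discriminate between tested women as printed. It is probably a unit slip. The number of women affected cannot be estimated, because the protocol does not say how many had signs of severe anaemia at the first visit or what limit the clinics used.

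The conclusion assumes that the list ending with the third-visit appointment is the second visit's, which its references back to the first visit support. It also assumes that no unseen first-visit item overrides the printed line.

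The week 30 against week 32 difference is minor. Table 3 calls its weeks approximate, and Table 2 links interventions to indicators rather than setting the schedule.

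**What to change.** The responsible clinical committee should:

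- reconcile the first-visit line (VII.B) and the second-visit line (VIII.A) to one value in one unit, consistent with the unit on the Summary form;
- check the Manual of Clinical Activities for the same line and correct it if it is there;
- notify any intervention clinic still applying the rule;
- for sites that have finished, record which limit was used. Khon Kaen closed recruitment in April 1997 and follow-up in October 1997, so a notice there would change nothing;
- as a minor edit, state one nominal week for the all-women haemoglobin test in Table 2(b) and the visit schedule.

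The cost is a few lines of text and a short note, with no extra women or tests. This review does not propose a threshold or a dose step.
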